The study includes 2020 adults (≥ 18 years old) who are planning to undergo elective non-cardiac surgery with ASA grade I-III under general anesthesia that requires tracheal intubation. The trial excludes patients for whom the intervention fluids is contraindicated or should be withhold by the judgement of the attending physician (known allergy to hydroxyethyl starch and/or multiple electrolyte injection; presence of renal failure preoperatively (defined as eGFR < 30 mL/min/1.73m 2 and/or patient receiving renal replacement therapy); abnormal coagulation function (PLT $< 100\times 10^9$ /L and/or PT $< 70\%$ and / or aPTT > 35 s); severe electrolyte disorder ($\text{Na}^+ > 160$ mmol/L and/or < 120 mmol/L); increased preoperative intracranial pressure requiring dehydration treatment). The trial also excludes patients with decompensate organ dysfunction or with systematic morbidities [cardiac dysfunction (EF $< 35\%$); liver dysfunction (defined as Child-Pugh C); morbid obesity (BMI > 37.5 kg/m 2 or > 32.5 kg/m 2 with metabolic diseases)]. Patients with anticipated length of postoperative hospital stay less than 24 hours and patients scheduled for multiple operations during this hospitalization (e. g. burn patients) are also excluded from the study.

Randomisation, Allocation, Concealment and Blinding

Permute-blocked randomisation with random block sizes stratified on study sites is used. The randomisation procedure was realised using a web-based service (Research Electronic Data Capture, RedCap, developed by Vanderbilt University).

Eligible patients will be assigned to receive either colloid or crystalloid before anaesthesia induction at 1:1 ratio. Participants, caregivers, and investigators responsible for analysing data and assessing outcomes are unaware of the group assignments. Only one investigator will be unblinded and prepare the allocated intervention fluid. The blinding is achieved by covering the intervention fluid with opaque sterilized cloth bag. The fluid infusion will be conducted and finished through an infusion pump (Zhejiang Smith Medical instrument Co., Ltd., SY-1200 Infusion Pump) prior to induction of anesthesia. The unblinded investigator will not be involved in any other aspect of the surgery, anaesthesia, data recording, outcome assessment, or data analysis.

Interventions

Patients will be administered 5 ml/kg 6% Hydroxyethyl Starch 130/0.4 Electrolyte injection or 5 ml/kg multiple electrolyte injection before anaesthesia

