In order to detect a 13% absolute reduction (from 33% to 26%) for the primary outcome of postoperative complications of Clavien-Dindo Grade \geq I up to 30 days after surgery (a risk ratio of 0.8), with 90% power and an overall type I error rate of 5%, a total of 2020 patients (1010 per arm) are required, accounting for 10% drop-out rate.

Randomisation procedure

Randomisation will occur after obtaining informed consent from the eligible patients and shortly before the index surgical procedure is due to start (last-minute randomization). Patients will be centrally allocated to treatment arms in a 1:1 ratio by permuted block randomization stratified with participant centers. To enter a patient into the COIN trial, research staff at each participant site will log on to a secure web-based randomization platform of Redcap data

entry system and obtain a unique patient identification number and allocation assignment. This information will be only revealed to the unblinded investigator who prepare the intervention fluids.

Datasets for Analyses

All statistical analyses within this study will be performed following the intention-to-treat principle. This implies that patients will be analysed in accordance with the treatment groups to which they were initially assigned, as depicted in Figure 1. It is expected that there will be either no or very minimal losses to follow-up for primary and secondary outcomes considering the prospective feature. Patients with missing primary outcome data will be excluded from the analysis (complete-case analysis approach). Missing data for baseline covariates to be included in the analysis model will be accounted for using multiple imputation.

Participation of individual patient in the study will be terminated if they (or their trusted person) withdraw consent. However, if the investigator discontinues the patient's participation, either temporarily or permanently, for reasons in the patient's best interest, especially when serious adverse events are suspected to be related to the intervention, the patient will remain in the analysis to uphold the intention-to-treat principle. Their data will continue to be collected until 30 days after surgery, which marks the final follow-up.

Modified Intent-to-Treat (m-ITT) population excludes individuals who had their

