For all analyses, a significance level of 5% will be used. Multiple comparisons will be conducted without Type I error correction and will be interpreted as exploratory.

Data Presentation and Baseline characteristics

Baseline characteristics will be summarized using descriptive statistics for whole patients cohort and for each treatment group by mean and standard

deviation or median and interquartile range for continuous variables, and the number, frequencies, and percent for categorical variables.

Durations According to Dates

For the indexed surgery, the date of randomization or admission to the intensive care unit corresponding to the surgery date will serve as day 1.

Take, for example, the calculation of the postoperative hospital stay (in days).

The formula is: (Discharge date from hospital - Date of index surgery) + 1

Exact dates will be tracked and documented.

Analysis of the primary endpoints

The primary endpoint, incidence of postoperative complications as defined by higher than grade I Clavien-Dindo classification at 30 days after surgery will be analyzed using Chi-squared test as crude analysis. Unadjusted risk ratios with 95% confidence intervals will be estimated by two-by-two table with the use of log-Normal approximation or other approximation/numeric methods as appropriate. The effect size will be expressed as risk differences (95% confidence intervals) will be estimated using Wald's likelihood ratio approximation test or other methods appropriate, with the number needed to treat as the reciprocal of the risk difference, rounded to the nearest integer.

Secondary Analyses of the primary endpoint

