To account for potential confounders, the adjusted analysis of primary endpoint will use a logistic regression model, where the primary endpoint as the dependent variable and independent variables to include study group (colloid fluid bolus group vs crystalloid fluid bolus group), adjusting for the relevant confounders (planned surgical procedure complexity grade, ASA grade, gender, age, baseline hemoglobin, and baseline creatinine, NPO duration, fluid administration within 12 hours prior to surgery). Odds ratios (95% confidence intervals) will be reported; for those ORs may potentially be biased approximation for RRs, estimates will be obtained via either binomial regressions or converted using bootstrap methods. We will also develop a logistic regression model accounting for the above variables plus any baseline characteristics that appear on visual review to be potentially imbalanced between the study groups.

To account for the center effects, we will fit a mix-effect model with the primary outcome as dependent variable, including group assignment as a fixed effect and participant center (stratification variable) as a random effect. Potential confounders that included in the model are the same as the logistic regression model. Alternative method to use if mixed-effect models fail to reach convergence:

- Include participant sites as a fixed-effect instead of random effect.
- Remove the fixed effect for participant sites
- Adjust for age, hemoglobin, creatinine, fasting duration, etc as a single

continuous variable.

- Remove the covariates in prespecified order to see if convergence reached: gender, hemoglobin, creatinine, age, surgical complexity, ASA grade.

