The COIN trial is to evaluate whether colloid bolus infusion before anesthesia induction improves clinical outcomes compared to crystalloid bolus infusion in patients undergoing non-cardiac surgery under general anaesthesia. In clinical practice, in rare circumstance, surgery may be delayed or canceled, and the participant may not undergo surgery before the outcome is collected. Similarly, in rare instances, the surgery may be conducted under local anesthesia. These participants will be excluded and the left participants who undergo surgery will be analyzed as mITT datasets.

Protocol Deviations

The number and percent of patients with at least one protocol deviation will be summarized for each treatment arm. These include received wrong fluid, received wrong dose of fluid, or with infusion duration exceeds 15 min. These participants will be excluded and the left participants will be analysed as PP datasets.

Analysis of the secondary endpoints

Incidence of hemodynamic instability within 20min of anesthesia induction.

Incidence of post-induction hypotension will be analysed using a logistic regression model, adjusting for ASA grade, gender, age, NPO duration, fluid administration within 12 hours prior to surgery (y/n), history of hypertension.

Intraoperative consumption of vasopressors

Intraoperative consumption of vasopressors will be analyzed using a linear regression model, adjusting for ASA grade, gender, age, NPO duration, fluid administration within 12 hours prior to surgery (y/n), history of hypertension.

Length of postoperative hospital stay

Length of postoperative hospital stay will be analysed using a competing-risk time-to-event model, considering mortality as a competing risk for hospital discharge. The model will include adjustment for planned surgical procedure complexity grade, ASA grade, gender, age, baseline hemoglobin, and baseline creatinine. In case of convergence issues, singular matrix, or other numeric complexity, appropriate data transformation, or dimension reduction methods will be used.

For each treatment arm, we will present median and IQR for length of hospital stay for patients survived to hospital discharge. The number and percentage of patients survived to discharge and number and percentage of patients who died will also be reported.

Rate of ideal postoperative recovery within 5 days of surgery

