Rate of ideal postoperative recovery within 5 days of surgery will be analysed using a logistic regression model, adjusting for planned surgical procedure complexity grade, ASA grade, gender, age, baseline hemoglobin, and baseline creatinine. Similar will be conducted for as above for cases of computing complexities.

Analyses of exploratory outcomes

Each individual component of the composite primary endpoint (by organ system and by different Clavien-Dindo classification Grades)

This will be analyzed using the same approach as for the analysis of the primary outcome above. Unadjusted Chi - squared test will be used.

Thirty day all-cause mortality

The expected event rate for this endpoint is extremely low. Thus, descriptive statistics will be used. Fisher exact test will be used to compare between group difference.

Incidence of unplanned ICU admission;

This outcome will be compared either using Chi-square test or Fisher exact test as appropriate depending on rate.

Incidence of unplanned reoperation

This outcome will be compared either using Chi-square test or Fisher exact test as appropriate depending on rate.

Incidence of in-hospital complications

This outcome will be compared either using Chi-square test or Fisher exact test as appropriate depending on rate.

Barthel index for activities of daily living (ADL) at 30 days after surgery.

The ADL score will be analyzed using a linear mixed model, with a random intercept for participant centers and adjusting for planned surgical procedure complexity grade, ASA grade, age, gender, baseline hemoglobin, and baseline creatinine. For any computation complexities, variable transformations or dimension reduction methods will be used.

Clavien-Dindo Grade IV - V complications within 30 days of surgery

Clavien-Dindo Grade IV - V complications within 30 days of surgery will be analyzed using a logistic regression model, adjusting for planned surgical procedure complexity grade, ASA grade, baseline hemoglobin, and baseline creatinine.

The expected event rate for this endpoint is lower than for other outcomes, thus we reduce the number of covariates that included in the model.

Analysis of Safety outcomes

Safety outcomes will be analyzed using the same method as the analysis of primary endpoints.

Interim analyses and stopping rules

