Prespecified subgroup analyses using formal tests of statistical interaction in a logistic regression model will be performed for the primary outcome to assess whether prespecified baseline variables modify the effect of treatment group on the primary outcome intervention differs among subgroup population. The subgroup analyses will be performed using the same model as for the primary endpoint. Independent variables will include study group assignment, the potential effect modifier of interest, and adding an interaction term between the two, aka the potential effect modifier and the treat arm. The presence of interaction will be tested using a likelihood ratio test comparing the subgroup

analysis model with interaction term, to the primary analysis model without interaction term. The test will be considered significant at the 5% level. A P value for the interaction will be reported. P values less than 0.1 will be considered potential interaction, while values less than 0.05 considered to a confirmed interaction. Non-linearity for continuous variables will be explored and analyzed using smoothed methods such as splines and preferably consider 3-5 knots using a locally weighted regression or partial effects plots.

Patients with complete outcome data will be included in the subgroup analysis. Within each subgroups, we will report summary statistics of the outcome by treatment arm, and a treatment effects and 95% confidence intervals. We will use a forest plot to display the effect of covariates. For presenting the continuous variables, they will be dichotomous for forest plot demonstration.

The pre-specified subgroups are:

- Participant center (1-7)
- age (continuous variable, and < 65 years vs ≥ 65 years)
- gender (male, female)
- BMI (continuous variable, and $< 24 \text{ kg/m}^2$ vs $\geq 24 \text{ kg/m}^2$)
- ASA classification (I, II ,III)
- Surgical procedure (abdominal, reproductive and urogenital system, musculoskeletal and connective tissue, breast & thyroid, facial and orthognathic surgery and ophthalmology, nervous system, other)
- Surgical complexity grade (minor, moderate, major, complex)

- NSQIP any complication risk (continuous variable)
- Inferior Vena Cava Collapsibility Index (continuous variable)
- Baseline SBP (continuous variable)
- NPO duration (continuous variable)
- Fluid administration at 12 hours prior to surgery

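### The only confirmatory test ignores the centre stratification used at randomisation; it is valid but slightly conservative, and a centre-stratified test would cost nothing

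*SAP*

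**What the plan says.** On allocation, the SAP section Randomisation, Allocation, Concealment and Blinding states: "Permute-blocked randomisation with random block sizes stratified on study sites is used". The section Randomisation procedure repeats this: "Patients will be centrally allocated to treatment arms in a 1:1 ratio by permuted block randomization stratified with participant centers". The section Ethics and Study Design gives seven hospitals.

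On analysis, the section Analysis of the primary endpoints says that the endpoint "at 30 days after surgery will be analyzed using Chi-squared test as crude analysis", with unadjusted risk ratio and risk difference. Under Corrections for Multiple Testing this is the single primary analysis and everything else is exploratory.

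Centre appears elsewhere, but unevenly:

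- Secondary Analyses of the primary endpoint: the adjusted logistic model lists eight covariates and omits centre. A further model includes centre as a random effect: "To account for the center effects, we will fit a mix-effect model with the primary outcome as dependent variable". If it does not converge, the listed alternatives are to make site a fixed effect, then "Remove the fixed effect for participant sites", and only later to drop covariates.
- Analysis of the secondary endpoints: the models omit centre, for example "Incidence of post-induction hypotension will be analysed using a logistic regression model, adjusting for ASA grade, gender, age, NPO duration".
- Analyses of exploratory outcomes: the Barthel index model does include it: "The ADL score will be analyzed using a linear mixed model, with a random intercept for participant centers".
- Subgroup analyses: "The subgroup analyses will be performed using the same model as for the primary endpoint". The interaction test is made against a primary analysis model, but the primary analysis is a test of a two-by-two table, not a model.

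**The concern.** Blocking within centre keeps the arms nearly equal in each hospital. Differences between hospitals then cancel out of the comparison of arms. The crude chi-squared variance does not know this and still counts between-centre variation as noise. The consequence is a P value somewhat too large and an interval somewhat too wide whenever centres differ.

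What is at stake is efficiency, and agreement between design and analysis. There is no bias and no inflation of type I error. Leaving out covariates that were not used to stratify does not affect the size of the test either.

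**Working it through.** **The plan's own figure.** Inputs from Sample Sizes: 33% against 26%, 90% power, overall type I error 5% (two-sided P value under General analysis Principles), 10% drop-out, 1010 per arm. The pooled two-proportion formula is

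n = [1.96·√(2·0.295·0.705) + 1.2816·√(0.33·0.67 + 0.26·0.74)]² / 0.07² = (1.264 + 0.824)² / 0.0049 ≈ 890 per arm.

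Then 890/0.9 ≈ 989 per arm, 1978 in total, within 3% of 2020. The stated size is thus consistent with an unstratified calculation.

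**How conservative the crude test is.** Let p_k be the rate in centre k and p̄ the mean over equal centres. With balanced arms in each centre, the true variance of the crude difference is a fraction r of the variance the crude test assumes:

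r = mean of p_k(1−p_k) / [p̄(1−p̄)] = 1 − V/[p̄(1−p̄)], where V is the between-centre variance of p_k.

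For seven evenly spaced rates with spacing s, V = s²·(7²−1)/12 = 4s². For 21-45%, s = 0.04, V = 0.0064 and r = 1 − 0.0064/0.2211 = 0.971.

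With the crude test planned at 90% power (1.96 + 1.2816 = 3.2416):

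- crude type I error = 2[1 − Φ(1.96/√r)]
- crude power = Φ(1.2816/√r)
- stratified power = Φ(3.2416/√r − 1.96)
- excess interval width = 1/√r − 1

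| Control rates (assumed) | r | Crude type I error | Crude power | Stratified power | Excess width |
|---|---|---|---|---|---|
| all 33% | 1.000 | 5.0% | 90.0% | 90.0% | 0 |
| 28-38% | 0.995 | 4.9% | 90.1% | 90.1% (gain 0.1 point) | 0.3% |
| 21-45% | 0.971 | 4.7% | 90.3% | 90.8% | 1.5% |
| 15-55% (mean 35%) | 0.922 | 4.1% | 90.9% | 92.2% | 4.2% |

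**Check by simulation.** With 7 × 260 patients, blocks of 4 within centre and 20,000 runs, type I error (crude/Cochran-Mantel-Haenszel) in the same four settings was 5.0/5.0, 5.2/5.2, 4.5/4.8 and 4.0/4.9%. The power gain at a risk ratio of 0.8 was 0.0, 0.1, 0.5 and 1.2 points.

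A larger simulation (400,000 runs, 33% against 26.4%) spread the centres on the logit scale. Its power starts near 87% because a risk ratio of exactly 0.8 gives 26.4%, for which 909 evaluable patients per arm yield 86.9%.

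| Between-centre SD (logit) | Centre rates | Type I error, crude / stratified | Power, crude / stratified |
|---|---|---|---|
| 0 | 33% | 5.0 / 5.0% | 87.0 / 86.9% |
| 0.3 | 23-44% | 4.8 / 5.0% | 87.2 / 87.6% |
| 0.5 | 18-51% | 4.4 / 5.0% | 87.6 / 88.5% |
| 1.0 | 8-68% | 3.1 / 4.9% | 89.0 / 92.0% |

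Unequal centre sizes gave smaller gains (SD 0.5: 87.4 / 88.2%).

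**Does stratifying change what is estimated?** The Mantel-Haenszel weight for the risk difference in a centre is n₁n₀/(n₁+n₀). With equal arms in a centre of size n this is n/4, proportional to centre size, so the weighted difference equals the crude one. The same cancellation makes the two risk ratios equal. Under near-balance the point estimates hardly move; it is the variance that is corrected.

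**Covariates, a separate matter.** Adjusting for one covariate with an assumed log-odds of 0.3, 0.6 or 0.9 per SD (1818 patients, 33% against 26.4%, 6,000 runs) moved power from 87.2 to 88.1, 86.4 to 88.3 and 87.4 to 91.4%. Type I error was 4.7-5.3% for both tests. This bears only on the regression alternative in the fix.

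**The case against.** The strongest reply is that nothing here is wrong. The test is prespecified, valid, matches a marginal risk difference and agrees with an unstratified sample size. Crude power never falls below plan in these scenarios; it is lower only than that of a better test. A centre-adjusted model is also reported, and centre is a listed subgroup. The gain is small in absolute terms: with 909 per arm the half-width of the risk-difference interval is 1.96·√[(0.2211 + 0.1924)/909] ≈ 4.2 points, so an excess of 0.3, 1.5 or 4.2% is about 0.01, 0.06 or 0.18 point. The largest gain in the first table needs centres from 15% to 55%, and the SAP gives no centre rates.

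All of that stands, and it is why the point is optional. It does not supply a reason to omit the stratification factor from the one test that counts. The centre-adjusted model is exploratory, and its listed alternatives include removing the effect it was built to capture.

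Two further replies deserve weight. The futility rule is stated on a z-score, so a change of primary test must say which z applies. The SAP is dated 19 January 2025, shortly before the planned end of accrual on 31 March 2025, so the change must be made and dated before unblinding. Both add wording, not data. On the fallback list, only the covariate item is expressly ordered, so the sequence is a matter of reading. The reference model for the subgroup tests can probably be inferred, but it should be named.

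**Conclusion.** The concern holds as a minor point of efficiency. The confirmatory test leaves out the factor that restricted randomisation and is conservative to the extent that centres differ. The cost is nothing if centres are alike, about 0.5 power point for control rates of 21-45%, and about 1.3 points for 15-55%; only more extreme spreads give more. These figures rest on assumed centre rates, equal centre sizes and near-balance within centre. The stratified test held about 5% throughout and lost no measurable power when centres were identical. Validity of the planned result is not in question.

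**What to change.** Before unblinding:

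1. Name a Cochran-Mantel-Haenszel test stratified by centre as the primary analysis, with Mantel-Haenszel risk ratio and risk difference and 95% intervals. Keep the crude chi-squared test as supportive. An acceptable alternative is logistic regression with the covariates already listed plus fixed centre effects, standardised to a marginal risk ratio and risk difference.
2. State whether the futility z-score is crude or stratified, and if that look has already been taken, which was used.
3. In the non-convergence list, drop covariates before centre.
4. Add centre to the secondary-endpoint models.
5. Under Subgroup analyses, name the reference model so that it agrees with the chosen primary analysis.

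The cost is SAP wording and a few lines of code, with no new data and no change to sample size or estimand.

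### The adjusted models for length of stay, ideal recovery and (as a secondary analysis) the primary endpoint leave out two listed baseline variables, NSQIP risk and procedure category: a minor loss of efficiency that does not touch the primary test

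*SAP*

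**What the plan says.** **Primary endpoint.** Under Analysis of the primary endpoints, the SAP plans a crude chi-squared test with an unadjusted risk ratio and risk difference. Under Secondary Analyses of the primary endpoint it adds a logistic model, "adjusting for the relevant confounders (planned surgical procedure complexity grade, ASA grade, gender, age, baseline hemoglobin, and baseline creatinine, NPO duration" and fluid given in the 12 hours before surgery. A mixed model with centre as a random effect uses the same covariates. A further logistic model adds any baseline variable that looks imbalanced once the arms are inspected.

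**Secondary endpoints.** For length of stay, a competing-risk model: "The model will include adjustment for planned surgical procedure complexity grade, ASA grade, gender, age, baseline hemoglobin, and baseline creatinine". For ideal recovery within 5 days, an analysis "using a logistic regression model, adjusting for planned surgical procedure complexity grade, ASA grade, gender, age, baseline hemoglobin, and baseline creatinine".

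**Subgroup analyses.** The variables, which the section describes as prespecified and baseline, include "NSQIP any complication risk (continuous variable") and "Surgical procedure (abdominal, reproductive and urogenital system, musculoskeletal and connective tissue, breast & thyroid" and further categories, seven in all. Effect modifiers collected after randomisation are listed separately.

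**Status.** Corrections for Multiple Testing declares one primary analysis of one primary outcome and calls everything else exploratory.

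**The concern.** The primary endpoint is any complication within 30 days, and NSQIP risk is by name a patient-level prediction of any complication. The three models describe the operation only by a complexity grade, although the surgery ranges from breast and thyroid to abdominal and nervous system.

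A baseline predictor left out of a logistic or time-to-event model pulls the treatment coefficient towards zero and costs power. Stay and ideal recovery are the most exposed. Both depend on when the patient is discharged, which plausibly differs by specialty, and the section for each plans no crude comparison beside the adjusted model. (General analysis Principles names crude tests in general terms, but the endpoint sections are more specific. For stay they add only descriptive medians by arm.)

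The model driven by observed imbalance is no substitute. It lets a variable in because of how the arms happen to look, not because it predicts the outcome, and only after the data are seen.

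**Working it through.** **1. The plan's own sample size.** Inputs from Sample Sizes: 33% versus 26%, 90% power, 5% type I error (two-sided, from General analysis Principles), 10% drop-out, 1010 per arm. The section calls the difference a 13% absolute reduction, but 33 − 26 = 7 points, which is used here.

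n per arm = [1.96·√(2·0.295·0.705) + 1.2816·√(0.33·0.67 + 0.26·0.74)]² / 0.07² = (1.264 + 0.824)² / 0.0049 ≈ 890.

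890/0.9 = 989 per arm, 1978 in total; with continuity correction 919 per arm, 2044 in total. The stated 2020 lies between them.

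**2. Primary test.** Evaluable per arm: 1010 × 0.9 = 909. Power = Φ[(0.07·√909 − 1.264)/0.643] = Φ(1.316) = 90.6%. No covariate enters, so the additions change nothing here.

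**3. Room in the models.** Expected primary events: 909 × (0.33 + 0.26) ≈ 536. Current model terms: treatment 1, complexity 3, ASA 2, and six single-parameter covariates, 12 in all; 536/12 ≈ 45 events per parameter. With NSQIP risk, 536/13 ≈ 41. With six category terms as well, 536/19 ≈ 28. Overfitting is no obstacle.

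**4. Gain in the adjusted primary-endpoint model.** Simulation with 1818 patients, 33% versus 26%, 2000 replicates. The current covariates act as one score (0.6 or 0.9 log-odds per SD). What the new variables add independently acts as a second score (0 to 0.8 per SD). These strengths are assumptions.

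| Current score | Added score | AUC | Power, current → extended (%) | Variance ratio for the standardised risk difference |
|---|---|---|---|---|
| 0.6 | 0 | 0.659 → 0.659 | 92.5 → 92.4 | 1.000 |
| 0.6 | 0.2 | 0.659 → 0.667 | 92.2 → 92.8 | 0.995 |
| 0.6 | 0.4 | 0.654 → 0.685 | 92.0 → 92.8 | 0.984 |
| 0.6 | 0.6 | 0.646 → 0.711 | 92.9 → 94.1 | 0.943 |
| 0.6 | 0.8 | 0.641 → 0.741 | 92.8 → 95.0 | 0.898 |
| 0.9 | 0.4 | 0.717 → 0.738 | 94.2 → 94.6 | 0.968 |
| 0.9 | 0.8 | 0.704 → 0.775 | 93.3 → 95.6 | 0.909 |

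The gain is 0 to about 2 points, and nil if the variables add nothing.

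**5. Odds-ratio scale.** At 0.6 and 0.6, the SE of the log odds ratio rises from 0.1068 to 0.1106, so the 95% interval widens from 3.92 × 0.1068 = 0.419 to 3.92 × 0.1106 = 0.434. The coefficient moves from −0.361 to −0.386, so |z| rises from 3.38 to 3.49. (3.49/3.38)² ≈ 1.07, in line with 1/0.943 = 1.06 for the standardised risk difference.

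**6. Stay and ideal recovery.** Simulation with 1818 patients, current covariates at 0.6 per SD, and seven equal procedure categories fitted as six indicators. Effective-sample gain = (mean z extended / mean z current)² − 1. NSQIP risk was not simulated separately here.

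- *Ideal recovery* (logistic, assumed event rate about 60%): category SD of 0, 0.5 and 0.8 log-odds gives gains of about 0, 5 and 13 to 15% over two runs. In one of them (800 replicates) power went from 78 to 78%, 82 to 84% and 79 to 84%. An SD of 0.8 means odds differing by e^0.8 ≈ 2.2 between categories one SD apart.
- *Stay* (proportional hazards for discharge, hazard ratio 1.15, no deaths simulated in the run whose power is given): category SD of 0 and 0.3 log-hazard gives gains of about 0 to 2% (no real gain) and 14 to 15%. In that run (500 replicates) power went from 83 to 82% and from 80 to 84%. An SD of 0.3 means discharge rates differing by e^0.3 ≈ 1.35.
- Stronger assumptions give more: 20% at 1.0 log-odds and 36% at 0.5 log-hazard. The SAP offers no basis for choosing them.

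**The case against.** The strongest reply is that nothing here is an error. The SAP adjusts to deal with confounding rather than to gain efficiency, its covariate list is fixed in advance and sensible, and these analyses are exploratory. Complexity grade, ASA grade, age and sex already carry part of what NSQIP risk and procedure category would supply. The SAP gives no figure for the rest, and its list of baseline data does not name NSQIP risk, so completeness is unknown. Six category terms would also strain models for which convergence fallbacks are already written.

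Most of this stands, and it limits the point to a minor improvement. It does not remove it: the variables are already committed to another analysis, and the models have room for them.

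A reader might infer more than the document supports:

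- *That the trial's main result loses power.* It does not; the primary test is unadjusted and sized that way.
- *That the adjusted model could gain four points.* One setting in a run of 1,500 simulated trials went from 90.7% to 94.8%. It needs the independent part of NSQIP risk (0.8 per SD) to outweigh all listed covariates together (0.5 per SD). The other four settings of that run gave 0.8 to 1.9 points.
- *That the odds ratio would be estimated more precisely.* Its interval widens slightly (step 5).
- *That the linear-regression rule 1/(1 − R²) gives the gain for stay.* The planned model is a competing-risk time-to-event model, to which that rule does not carry over directly.
- *That the change is free.* It costs little, but it does cost parameters.

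**Conclusion.** The point holds as a minor improvement. Both variables are named as baseline variables, and neither is in the covariate lists for the adjusted primary-endpoint, stay or ideal-recovery models. Only the data-driven imbalance model could admit them. The primary result is unaffected. The expected gain is about 0 to 2 power points for the adjusted primary-endpoint model and roughly 0 to 15% in effective sample size for stay and ideal recovery.

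These ranges rest on assumed prognostic strengths, an assumed ideal-recovery rate of about 60%, and a discharge model simplified to proportional hazards. If the variables predict nothing beyond the current covariates, the gain is nil and the loss negligible. The case is best for stay and ideal recovery, because no crude comparison stands beside the adjusted model in their sections.

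**What to change.** Amend the SAP before unblinding:

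1. Add NSQIP any-complication risk, on the logit scale (one parameter), to the logistic and mixed models for the primary endpoint. Give it a place in the covariate-removal order used when the mixed model fails to converge. Fasting duration and prior fluid have no place in that order either and could be added at the same time.
2. Add NSQIP risk and the seven-level procedure category, coded from the planned operation, to the stay and ideal-recovery models.
3. Beside each odds ratio, report a standardised risk difference or risk ratio, which is where a gain in precision would show. The SAP already allows risk ratios through binomial regression or bootstrap conversion.
4. Leave the Grade IV–V model as it is; its covariates were reduced on purpose because events are few.

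Cost: SAP wording, and up to seven extra parameters in the stay and recovery models (from about 10 to 17). If ideal recovery occurs in about 60%, the 0.4 × 1818 ≈ 727 patients without it give 727/17 ≈ 43 per parameter. The risk of non-convergence rises slightly, and the SAP's fallbacks already cover that. Missing values of either variable fall under the planned multiple imputation of covariates, but the completeness of NSQIP risk should be checked on blinded data first.
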